#### PROTOCOL Biomedical Research Saint Louis University

\_\_\_\_\_

Protocol Title:

SURGX antimicrobial gel versus povidone-iodine skin incision prep for the prevention of bacterial seeding in total shoulder arthroplasty

#### Subject Population(s) Checklist

Select All That Apply :

X Adults

Cognitively Impaired Subjects Employees (specifically targeted) Fetuses Minors (under 18) Neonates Non English Speaking Subjects Pregnant Women Prisoners Students (specifically targeted) Terminally III Subjects Wards of the State Other (any population that is not specified above)

\* \* \* Study Location \* \* \*

#### Study Location(s) Checklist

Indicate where the study will be conducted. Select all that apply: Saint Louis University, Medical Center Campus Saint Louis University, Frost Campus Saint Louis University, Madrid Campus Saint Louis University, SLUCare Practice Locations

X SSM STL (DePaul Hospital, St. Mary's Health Center, St. Joseph (St. Charles, Wentzville, Lake Saint Louis), St. Clare)

Cardinal Glennon Children's Medical Center

Saint Louis University Hospital (SSM Health- SLU Hospital)

SLU-SSM Cancer Center Research Alliance Sites

Other (In the box below, list any off-campus institutions or locations and describe the activities being conducted there. Please provide letters of cooperation and/or IRB approvals from each location to document support/approval of the study. You may provide such documentation as it becomes available, but you may not begin work at those sites until documentation of support is provided to the IRB.) Please refer to the Guidance for involving non-SLU institutions in human subject research.

\_\_\_\_\_

\* \* \* General Checklist \* \* \*

General Checklist

Select All That Apply :

e	-PROTOCOL	PROTOCOL Biomedical Research Saint Louis University	·	Protocol # 32325 [name]
Pro	otocol Title:	SURGX antimicrobial gel versus pov bacterial seeding in total shoulder ar	vidone-iodine skin incision prep for throplasty	r the prevention of
х	Collection of Specimens Data collection via e-ma Deception/Incomplete D Dietary Supplements Vi	il or the Internet isclosure tamins, and Other Food Agents		
X X	FDA Approved Device FDA approved drugs, re studied), or biologic proc Genetic Testing HIV Testing	agents, other chemicals administered	to subjects (even if they are not b	being
х	Human blood, cells, tiss International Research o Investigational drugs, rea Investigational Device	ues, or body fluids or Research on International Populatio agents, chemicals, or biologic product	ins is	
X X	Investigator Initiated Stu Medical Records Photography, Video, or V Questionnaires and/or te Radioisotopes/radiation- rDNA/Gene Transfer The Registry(ies) Specimens to be stored Study of existing data or	dy *?HELP?* Voice-Recording Subjects ests producing machines, even if standard erapy for future research projects (must be in specimens	l of care in consent form)	
x	University Indemnified S Other (clarify in text box Single Use. Provide a br refer to research. For Sin	tudy (SLU is responsible for liability control to the right)	overage) *?HELP?* Single Use Therapy. Note: This app that 'research' will mean 'therapy'.	plication will
		* * * Funding * * *		
Fun	ding Checklist			
	NONE			
	Funding - Industry Spon	sor		

Protocol Title:

SURGX antimicrobial gel versus povidone-iodine skin incision prep for the prevention of bacterial seeding in total shoulder arthroplasty

#### \_\_\_\_\_

Sponsor Name	Sponsor's Protocol Version Date
Next Science	

NOTE: Applicable grant application, contract or subcontract, investigator's brochure, and sponsor's protocol (for all industry sponsored clinical trials) must be attached. You will be prompted for these in section #16 (Attachments).

#### \* \* \* Expedited Paragraphs \* \* \*

To request an Expedited Review, check the appropriate category(ies) below. Provide justification for your request for Expedited Review.

\_\_\_\_\_

To qualify for expedited review, research activities must (1) present no more than minimal risk to human subjects, and (2) involve only procedures listed in one or more of the categories below.

- 1. Clinical studies of drugs and medical devices only when condition (a) or (b) is met.
- a) Research on drugs for which an investigational new drug application (21 CFR Part 31, 32) is not required. (Note: Research on marketed drugs that significantly increases the risks or decreases the acceptability of the risks associated with the use of the product is not eligible for expedited review.)
- b) Research on medical devices for which
  - (i) An investigational device exemption application (21 CFR Part 812) is not required; or
  - (ii) The medical device is cleared/approved for marketing and the medical device is being used in accordance with its cleared/approved labeling.
- 2. Collection of blood samples by finger stick, heel stick, ear stick, or venipuncture as follows:
- a) From healthy, nonpregnant adults who weigh at least 110 pounds. For these subjects, the amounts drawn may not exceed 550 ml in an 8-week period and collection may not occur more frequently than 2 times per week; or

From other adults and children, considering the age, weight, and health of the subjects, the collection procedure, the amount of blood to be collected, and the frequency with which it will be collected. For these subjects, the amount drawn may not exceed the lesser of 50 ml or 3 ml per kg in an 8-week period and collection may not occur more frequently than 2 times per week.

#### PROTOCOL Biomedical Research Saint Louis University

Protocol Title:

SURGX antimicrobial gel versus povidone-iodine skin incision prep for the prevention of bacterial seeding in total shoulder arthroplasty

kg in an 8-week period and collection may not occur more frequently than 2 times per week.

\_\_\_\_\_

Children are "persons who have not attained the legal age for consent to treatments or procedures involved in the research, under the applicable law of the jurisdiction in which the research will be conducted."

3. Prospective collection of biological specimens for research purposes by non-invasive means.

EXAMPLES: (a) hair and nail clippings in a nondisfiguring manner; (b) deciduous teeth at time of exfoliation or if routine patient care indicates a need for extraction; (c) permanent teeth if routine patient care indicates a need for extraction; (d) excreta and external secretions (including sweat); (e) uncannulated saliva collected either in an unstimulated fashion or stimulated by chewing gumbase or wax or by applying a dilute citric solution to the tongue; (f) placenta removed at delivery; (g) amniotic fluid obtained at the time of rupture of the membrane prior to or during labor; (h) supra-and subgingival dental plaque and calculus, provided the collection procedure is not more invasive than routine prophylactic scaling of the teeth and the process is accomplished in accordance with accepted prophylactic techniques; (i) mucosal and skin cells collected by buccal scraping or swab, skin swab, or mouth washings; (j) sputum collected after saline mist nebulization.

4. Collection of data through non-invasive procedures (not involving general anesthesia or sedation) routinely employed in clinical practice, excluding procedures involving X-rays or microwaves. Where medical devices are employed, they must be cleared/approved for marketing. (Studies intended to evaluate the safety and effectiveness of the medical device are not generally eligible for expedited review, including studies of cleared medical devices for new indications.)

EXAMPLES: (a) physical sensors that are applied either to the surface of the body or at a distance and do not involve input of significant amounts of energy into the subject or an invasion of the subjects' privacy; (b) weighing or testing sensory acuity; (c) magnetic resonance imaging; (d) electrocardiography, electrocephalography, thermography, detection of naturally occurring radioactivity, electroretinography, ultrasound, diagnostic infrared imaging, doppler blood flow, and echocardiology; (e) moderate exercise, muscular strength testing, body composition assessment, and flexibility testing where appropriate given the age, weight and health of the individual.

- 5. Research involving materials (data, documents, records, or specimens) that have been collected, or will be collected solely for nonresearch purposes (such as medical treatment or diagnosis). (NOTE: Some research in this category may be exempt from the HHS regulations for the protection of human subjects. 45CFR 46.101(b)(4). This listing refers only to research that is not exempt.)
- 6. Collection of data from voice, video, digital, or image recordings made for research purposes.
- 7. Research on individual or group characteristics or behavior (including, but not limited to, research on perception, cognition, motivation, identity, language, communication, cultural beliefs or practices, and social behavior) or research employing survey, interview, oral history, focus group, program evaluation, human factors evaluation, or quality assurance methodologies. (NOTE: Some research in this category may be exempt from the HHS regulations for the protection of human subjects. 45 CFR 46.101(b)(2) and (b)(3). This listing refers only to research that is not exempt.)

|--|

Protocol Title:

SURGX antimicrobial gel versus povidone-iodine skin incision prep for the prevention of bacterial seeding in total shoulder arthroplasty

8. [FOR IRB use only]. Continuing review of research previously approved by a convened IRB only when condition (a), (b), or (c) is met.

\_\_\_\_\_

- a) Previously approved research where
  - (i) The research is permanently closed to the enrollment of new subjects;
  - (ii) All subjects have completed all research-related interventions; and
  - (iii) The research remains active only for the long term follow-up of subjects.
- b) Previously approved research where no subjects have been enrolled and no additional risks have been identified.
- c) Previously approved research where the remaining research activities are limited to data analysis.
- 9. [FOR IRB use only]. Continuing review or research not conducted under an investigational new drug application or investigational drug exemption where expedited categories two (2) through eight (8) do not apply but the IRB has determined and documented at a convened meeting that the research involves no greater than minimal risk and no additional risks have been identified.

## \* \* \* Background, Purpose, Study Procedures \* \* \*

#### Title

SURGX antimicrobial gel versus povidone-iodine skin incision prep for the prevention of bacterial seeding in total shoulder arthroplasty

Complete Sections 1 - 16. In sections that allow reference to sponsor protocol or grant, clearly state section and page numbers. Any information that is different or specific to the local site should be in the SLU application. Specify N/A as appropriate.

1. Background

Page numbers from a sponsor's protocol/grant may be referenced in 1a and 1b.

a) Provide an introduction and background information. Describe past experimental and/or clinical findings leading to the formulation of the study, if applicable. Investigator Initiated studies must cite references in the response provided or attach a bibliography. \*?HELP?\*

Cutibacterium acnes (C. acnes) prosthetic joint infection is a devastating and somewhat unique complication to shoulder arthroplasty. It is a very slow-growing, aerotolerant anaerobic, non-spore forming, gram-positive rod-shaped bacteria that takes up to 2-3 weeks to grow in a lab setting. There have been several studies assessing various agents in the fight to prevent C. acnes prosthetic joint infection. These agents include standard peri-operative measures typically taken when performing shoulder replacement surgery - pre-operative prophylactic antibiotics, pre-operative skin cleanse/wash, topical adjuvants (povidone-iodine, chlorhexidine, etc.), and intra-operative antibiotic powders. The overall infection rate of shoulder arthroplasty has been cited to be between 0.9-2.9%, with C. acnes being the most common bacterium in shoulder arthroplasty periprosthetic infections. Morbidity and cost associated with shoulder prosthetic joint infection is extremely high, requiring multiple surgeries and months of treatment

#### PROTOCOL Biomedical Research Saint Louis University

Protocol Title:

SURGX antimicrobial gel versus povidone-iodine skin incision prep for the prevention of bacterial seeding in total shoulder arthroplasty

\_\_\_\_\_

to overcome the infection.

One of the main issues with C. acnes is its preferred location within the body, residing within the sebaceous glands of the hair follicles, deep to the epidermis where many preoperative topical preparations to cleanse the skin prior to surgery have little affect. These glands are commonly found around the shoulder and upper back, and lead to acne. C. acnes, along with other common prosthetic joint infection bacteria, quickly create a biofilm which is impenetrable to most antibiotic agents, further stressing the importance of prevention. Recently there have been studies analyzing the effects of Benzoyl Peroxide (BPO) on C. acnes as it relates to shoulder arthroplasty in an attempt to reduce this bacterial burden prior to surgery. There have been promising results with multi-day preparation skin cleansing with benzoyl peroxide. However, there are no studies looking at intra-operative skin incision preparations targeting the region of skin where the C. acnes bacteria resides. In vitro studies show SURGX antimicrobial gel (Next Science, Jasksonville, FL) results in a marked reduction of C. acnes in addition to other common bacteria affecting prosthetic joints. This gel uses citric acid to chelate the metallic bonds of biofilm. The bacteria are then destroyed by a combination of a high osmolarity environment coupled with a surfactant.

The first purpose of the study is to evaluate if a dermal layer preparation will reduce positive cultures of C. acnes after primary shoulder arthroplasty. There will be a control group consisting of no skin preparation. There will be two additional comparative groups. The second purpose of this study is to compare the use of standard povidone-iodine swab versus SURGX antimicrobial gel as an application into the dermal layer after the skin incision has been made with a skin knife to see if there is a reduction in bacterial burden in the superficial and deep tissues at the end of a primary shoulder arthroplasty. Superficial and deep cultures will be held in the lab for 2 weeks to identify if bacteria is present. Our hypothesis is that the SURGX antimicrobial gel will provide a greater reduction in bacterial burden compared to povidone-iodine within the deep tissues after primary shoulder arthroplasty.

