#### 2. Purpose of the study

a) Provide a brief lay summary of the project in <200 words. The lay summary should be readily understandable to the general public.

Comparing the growth of intra-operative tissue cultures of Cutibacterium Acnes after primary shoulder replacement when using a no-prep control group versus antimicrobial wound gel versus betadine applied to the skin layer after the skin incision has been made. Reducing the bacteria present in the deep tissues at the end of the surgery may prevent infections from developing in the future.

Page numbers from a sponsor's protocol/grant may be referenced in 2b and 2c.

b) List your research objectives (specific aims & hypotheses of the study).

\_\_\_\_\_

Protocol Title:

SURGX antimicrobial gel versus povidone-iodine skin incision prep for the prevention of bacterial seeding in total shoulder arthroplasty

Primary objective: skin incision preparation solution intraoperatively after the skin incision has been made will reduce the number of positive cultures after primary shoulder arthroplasty versus no intraoperative skin incision preparation. A control group with standard preoperative skin prep will be included. All patients will receive standard of care preoperative antibiotics and preoperative skin cleansing preparation prior to draping for surgery.

Hypothesis: the use of skin incision preparation solution will be more effective at reducing positive cultures compared to the control group and the SURGX antimicrobial wound gel will result in decreased C. acnes growth from intra-operative cultures when compared to the use of povidone-iodine.

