c) If the proposed study is a clinical trial where a drug, vaccine, device or other treatment is compared to a placebo group or comparison treatment group, what are the guidelines or endpoints by which early decisions regarding efficacy or lack of efficacy can be made? For example, it may be reasonable to stop enrollment on a study when efficacy has already been clearly demonstrated, to avoid unnecessary enrollments of additional subjects. Alternatively, it may be reasonable to stop enrollment when it is clear that efficacy will never be demonstrated, given the statistical power of the study as designed. Describe the guidelines that are in place to assist in making these determinations, if relevant to the proposed study.

It has been reported in the literature that standard preoperative antibiotics and skin preparation prior to draping for the surgery does not eliminate the presence of bacteria in the wound after total shoulder arthroplasty. It is not known if this will lead to an increased risk of infections long term or if this is an incidental finding. No studies have looked at prepping the skin incision after the incision has been made to reduce this potential bacterial burden. Theoretically, if the bacterial burden is reduced at the time of surgery, this may reduce the risk of late term infection if it were to occur. The control group will receive standard pre-op skin cleansing. Since the study endpoint is presence/absence of C. acnes in the cultures, and we only plan to enroll 60 patients, we do not expect to cease enrollment early.

d) Describe how data analysis will be performed (statistical tests, methods of evaluating data) and indicate the smallest group/unit for which separate reporting will occur. For studies involving a questionnaire, if data and reliability information are available, please describe or provide references. For full board, unfunded studies describe sample size determination and power analysis. If none, please justify.

Statistics will be run through standard statistical programs, involving analyses that compare two groups of results - T-test, Chi-square etc. Our decision of sample size is based upon the literature with prior studies including comparative treatment groups of roughly 20 patients in each arm.

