There is no standard of care in regards to skin/dermis preparation for shoulder arthroplasty at SLU or in the field of shoulder replacement surgery. Common skin/dermis preparations include preoperative skin cleansers, betadine preparation, chlorhexidine skin preparation, and intraoperative irrigation with various solutions. All patients will receive standard pre-operative prophylactic antibiotics. They will all receive the same preoperative skin preparation with Hibiclens (chlorhexadine) and ChloraPrep (2% chlorhexadine gluconate / 70% isopropyl alcohol solution) prior to draping. Intra-operative irrigation will be standardized with Irrisept (chlorhexidine gluconate 0.05% in sterile water). During the study, the control group will not receive a skin incision prep after the incision is made while the other treatment groups will receive either povidone-iodine skin incision prep or SurgX gel prep. We are only looking for the presence of bacteria at the conclusion of the study. It is not known if this bacteria is clinically important but if present could potentially present as a late term infection. These infections may not present themselves for 2-10 years postoperatively. The assessment in this study is to see if this bacterial presence can be reduced after shoulder arthroplasty with the theoretical potential advantage of reducing late term infections. Patients will have standard of care follow up appointments with their physician which are typically at 2-weeks, 6-weeks, 3 months, 6 months, and yearly (no end date) following shoulder arthroplasty. These are not part of the research study.

g) Does this study involve any diagnostic imaging, labwork or genetic testing that could Y result in clinical discovery (diagnoses, genetic mutations, etc.)? Note that this could include discovery that is expected (related to the research) or incidental (not related to research aims, but possible, like a mass/shadow found in imaging despite not looking for it).

If yes, please describe and include whether there are plans to share findings with study participants.

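### The SURGX versus povidone-iodine hypothesis is about bacterial burden, but the only endpoint described is presence or absence of C. acnes, so a partial reduction would be understated and could be missed.

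*Combined protocol and SAP*

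**What the plan says.** The protocol describes the comparison of the two agents as a question of amount. In section 1a (Background) the second purpose is "to see if there is a reduction in bacterial burden in the superficial and deep tissues at the end of a primary shoulder arthroplasty", and the hypothesis is that "SURGX antimicrobial gel will provide a greater reduction in bacterial burden compared to povidone-iodine within the deep tissues". Section 2b (objectives and hypotheses) restates it as "SURGX antimicrobial wound gel will result in decreased C. acnes growth from intra-operative cultures when compared to the use of povidone-iodine", with no scale for growth.

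The read-out is described as yes or no. Section 1a says "Superficial and deep cultures will be held in the lab for 2 weeks to identify if bacteria is present". Section 3c says "the study endpoint is presence/absence of C. acnes in the cultures". Section 3f says "We are only looking for the presence of bacteria at the conclusion of the study".

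The comparison of any incision prep with none is worded differently. The primary objective in section 2b is that the prep "will reduce the number of positive cultures after primary shoulder arthroplasty versus no intraoperative skin incision preparation". Section 3b takes five cultures per patient, two superficial and three deep (one of these an implant swab), and plans to compare positive cultures between groups. Section 3d names the t-test and chi-square test without assigning either to an outcome.

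**The concern.** A yes/no culture result fits the primary objective, which concerns positive cultures. It does not fit the SURGX versus povidone-iodine hypothesis, which concerns how much bacteria remains. That comparison is between two active agents, where a difference of degree is a natural thing to look for.

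A culture can turn positive from a small residual inoculum. If specimens start well above the detection limit, an agent can remove most organisms and still leave many cultures positive. The trial would then show a smaller difference than the true one, or none. A report concluding that SURGX does not reduce burden more than povidone-iodine would go beyond what was measured.

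**Working it through.** **The plan's own figures.** Three groups of 20 give 60 patients, and 60 × 5 = 300 cultures. Both totals agree with sections 8b and 8j. The 20 per group rests on the size of earlier studies (section 3d), with no rate, effect, alpha or power, so it cannot be reproduced.

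**Inputs for the check**
- From the documents: three deep cultures per patient (section 3b), 20 per group (section 3b), and C. acnes present in up to 73% of cases (sections 3g and 10a).
- Assumed: organisms per specimen are Poisson; a culture is positive if it holds at least one organism; a patient is positive if any of three deep cultures is; 73% is the positivity in the reference arm; the true effect is a 90% cut in load. The loads are illustrative.

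**Formulas.** With mean load m per specimen, a culture is positive with probability 1 − exp(−m), and a patient with probability 1 − exp(−3m). If a fraction c of patients carry the organism, multiply by c. The mean number of positive deep cultures per patient is 3c(1 − exp(−m)).

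*Uniform low load (c = 1).* m = −ln(0.27)/3 = 0.436. After the cut m = 0.0436.
- Patient positive: 1 − exp(−3 × 0.0436) = 0.123.
- Mean count: from 3(1 − exp(−0.436)) = 1.06 to 3(1 − exp(−0.0436)) = 0.13.

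*Carriers at 10 per specimen (c = 0.73).* After the cut m = 1.
- Patient positive: 0.73(1 − exp(−3)) = 0.694.
- Mean count: from 0.73 × 3 = 2.19 to 2.19(1 − exp(−1)) = 1.38.

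*Carriers at 50 per specimen (c = 0.73).* After the cut m = 5.
- Patient positive: 0.73(1 − exp(−15)) = 0.730.
- Mean count: from 2.19 to 2.19(1 − exp(−5)) = 2.18.

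| Assumed load | Any deep culture positive, before → after | Mean positive deep cultures, before → after |
|---|---|---|
| 0.436, all patients | 73% → 12% | 1.06 → 0.13 |
| 10, carriers only | 73% → 69% | 2.19 → 1.38 |
| 50, carriers only | 73% → 73% | 2.19 → 2.18 |

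The same 90% cut appears as a fall of 61 points, 4 points or 0. At the middle load the count of positive deep cultures falls by 37% (1 − 1.38/2.19), although the any-positive rate barely moves. At the highest load the count saturates too.

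**When loads vary between patients.** A simulation used lognormal loads, three cultures, reference positivity set to 73%, 20 per arm, a 90% cut and 1,500 runs per setting. Tests were two-sided at 0.05 (assumed): Fisher's exact test on any-positive, and t-tests on the count and on the log10 organism count.

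| Between-patient SD (log10) | Any positive after cut | Power: any positive | Power: count 0–3 | Power: organism count |
|---|---|---|---|---|
| 0.5 | 22% | 0.86 | 0.98 | 0.98 |
| 1.0 | 39% | 0.46 | 0.74 | 0.77 |
| 1.5 | 49% | 0.24 | 0.44 | 0.48 |
| 2.0 | 55% | 0.15 | 0.26 | 0.27 |

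Here the effect is weakened but not removed, and the simple count recovers most of what full quantification would give. Part of the gap between the first and second power columns reflects the conservatism of Fisher's test at this sample size.

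**The case against.** The strongest reply is that this is mainly loose wording. The endpoint is stated plainly as presence/absence, the protocol moves freely between burden and presence, and the primary objective already refers to the number of positive cultures. Several cultures per patient give a crude graded measure, and the listed t-test would suit it. This has force: the count performs nearly as well as quantification in the simulation. But no section defines that count as the measure of burden or assigns it a test, and it saturates at high loads.

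The inputs can also be challenged, and fairly. The 73% is an upper figure and is not tied to deep cultures. The loads have no source in the documents. The any-of-three rule is not the plan's. The arithmetic compares treated with untreated patients, whereas the hypothesis compares two treatments. The results therefore show how widely the apparent effect can vary and do not predict it.

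Two stronger readings are tempting. A reader might infer that any large reduction short of eradication would be read as no effect. The documents do not support this: a lower load also lowers the chance that each culture is positive, and near-total loss arises only at loads far above the detection limit. A reader might also infer that no quantity is recorded for any specimen. That cannot be established, because the data collection sheet is listed in section 16 but was not supplied, and the content of the laboratory reports is unknown.

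**Conclusion.** The mismatch stands. Sections 1a and 2b put the SURGX versus povidone-iodine question in terms of burden or growth, while sections 1a, 3c and 3f describe only presence or absence, read after a 2-week hold. A partial reduction would be understated and could be missed, and a null result on presence would not show that burden was unchanged.

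The amount is uncertain. On the Poisson, any-of-three assumptions a 90% cut shows as a fall from 73% to between 12% and 73%; with loads varying between patients it shows as a fall to between 22% and 55%. All of these rest on assumed loads and on 73% as the reference rate. The small group size adds to the risk of missing an effect, but it is a separate matter. The point is a low-cost improvement to what the trial can conclude.

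**What to change.** Keep presence/absence as it is. Pre-specify one ordered burden measure per patient over the three deep cultures, compare SURGX with povidone-iodine on it by a rank test that allows for ties, and label it secondary.

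- **Minimum:** the number of positive deep cultures, 0 to 3. It needs no new data.
- **Refinement:** grade the positives by growth grade or day of first growth, if the laboratory already reports them. Check first whether the data collection sheet already holds them. Section 1a says the organism can take up to 2–3 weeks to grow, so no growth at 2 weeks should be described as none detected by then, not as zero burden.

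The cost is one more secondary analysis and possibly one or two data fields, with no extra cultures. A count of positives would still saturate at high loads, and the report should say so.

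If no burden measure is adopted, reword the hypothesis and the conclusion to culture positivity for C. acnes, and state in advance that a null result will not be interpreted as no reduction in burden. That costs only the rewording.
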